3.8.2. Analysis Visit Windows

Subject visits may not occur on protocol-specified days. Therefore, for the purpose of analysis, observations will be assigned to analysis windows.

In general, the baseline value will be the last nonmissing value on or prior to the first dose date of study drug, except for the mTSS baseline value. The mTSS baseline value will be derived based on the measurements collected on or prior to the first dose date of study drug + 14 days given the potential delay in scheduling an x-ray assessment. If multiple valid, nonmissing measurements exist in the analysis window as aforementioned, in general, the last nonmissing mTSS value on or prior to the first dose date of study drug will be selected as the baseline value; If all these multiple measurements occur at post first dosing, the value closest to the first dose date will be selected as the baseline value.

For subjects who were on placebo and then re-randomized, the baseline after Week 24 will be the last nonmissing value obtained on or prior to the first dose date of filgotinib, except for the mTSS baseline value. The mTSS baseline value will be derived based on the measurements collected on or prior to the first dose date of filgotinib + 14 days given the potential delay in scheduling an x-ray assessment. If multiple valid, nonmissing measurements exist in the analysis window as aforementioned, in general, the last nonmissing mTSS value on or prior to the first dose date of filgotinib will be selected as the baseline value; If all these multiple measurements occur at post first dosing of filgotinib, the value closest to the first dose date of filgotinib will be selected as the baseline value.

For efficacy endpoints, vital signs, ECG, weight, lipids and safety laboratory data, the analysis visit windows will be applied to data collected during the ‘on-treatment’ period. The ‘on-treatment’ period is defined as the last dose date of any study drug + 7 days.

The analysis windows for on-treatment efficacy endpoints including joint count assessment, HAQ-DI (including subject’s pain assessment), subject’s global assessment (SGA), physician’s global assessment (PGA), serum CRP , exploratory patient reported outcome (PRO), and vital signs, weight, and safety laboratory data (lipid data excluded) are provided in [Table 3-1](#) and [Table 3-2](#).

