Table 3-1. Analysis Visit Windows for On-Treatment Joint Count Assessment, HAQ-DI, SGA, PGA, CRP, Exploratory PRO, and Vital Signs, Weight, and Safety Laboratory Data (Lipid Data Excluded) for Subjects who were Initially Randomized to Filgotinib or Adalimumab, and Subjects who were Initially Randomized to Placebo and not Re-randomized

Analysis Visit	Nominal Study Day	Lower Limit	Upper Limit
Baseline	1	(none)	1
Week 2	15	2	22
Week 4	29	23	43
Week 8	57	44	71
Week 12	85	72	92
Week 14	99	93	106
Week 16	113	107	127
Week 20	141	128	155
Week 24	169	156	176
Week 26	183	177	197
Week 30	211	198	232
Week 36	253	233	281
Week 44	309	282	337
Week 52	365	338	≥ 365

Table 3-2. Analysis Visit Windows for On-Treatment Joint Count Assessment, HAQ-DI, SGA, PGA, CRP, Exploratory PRO, and Vital Signs, Weight, and Safety Laboratory Data (Lipid Data Excluded) for Subjects who were Initially Randomized to Placebo and Re-randomized

Analysis Visit	Nominal Study Day	Lower Limit	Upper Limit
Baseline	1	(none)	1
Week 2	15	2	22
Week 4	29	23	43
Week 8	57	44	71
Week 12	85	72	92
Week 14	99	93	106
Week 16	113	107	127
Week 20	141	128	155
Week 24	169	156	First Dose Date of Filgotinib - Study Day 1 + 1
Analysis Visit	On-Filgotinib Study Day	On-Filgotinib Lower Limit	On-Filgotinib Upper Limit
Week 26*	15	2	29
Week 30*	43	30	64
Week 36*	85	65	113
Week 44*	141	114	169
Week 52*	197	170	≥ 197

* For subjects who were on placebo and re-randomized their analysis window after Week 24 will be assigned according to On-Filgotinib Study Day, On-Filgotinib Lower Limit and On-Filgotinib Upper Limit.

The analysis windows for on-treatment mTSS and lipid data are provided in [Table 3-3](#), [Table 3-4](#), [Table 3-5](#), and [Table 3-6](#).

Table 3-3. Analysis Visit Windows for On-Treatment Lipid Data for Subjects who were Initially Randomized to Filgotinib or Adalimumab, and Subjects who were Initially Randomized to Placebo and not Re-randomized

Analysis Visit	Nominal Study Day	Lower Limit	Upper Limit
Baseline	1	(none)	1
Week 12	85	2	127
Week 24	169	128	267
Week 52	365	268	≥ 365

Table 3-4. Analysis Visit Windows for On-Treatment mTSS for Subjects who were Initially Randomized to Filgotinib or Adalimumab, and Subjects who were Initially Randomized to Placebo and not Re-randomized

Analysis Visit	Nominal Study Day	Lower Limit	Upper Limit
Baseline	1	(none)	15
Week 12	85	16	127
Week 24	169	128	267
Week 52	365	268	≥ 365

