Table 3-5. Analysis Visit Windows for On-Treatment Lipid Data for Subjects who were Initially Randomized to Placebo and Re-randomized

Analysis Visit	Nominal Study Day	Lower Limit	Upper Limit
Baseline	1	(none)	1
Week 12	85	2	127
Week 24	169	128	First Dose Date of Filgotinib - Study Day 1 + 1
Analysis Visit	On-Filgotinib Study Day	On-Filgotinib Lower Limit	On-Filgotinib Upper Limit
Week 52*	197	2	≥ 197

* For subjects who were on placebo and re-randomized their analysis window after Week 24 will be assigned according to On-Filgotinib Study Day, On-Filgotinib Lower Limit and On-Filgotinib Upper Limit.

Table 3-6. Analysis Visit Windows for On-Treatment mTSS data for Subjects who were Initially Randomized to Placebo and Re-randomized

Analysis Visit	Nominal Study Day	Lower Limit	Upper Limit
Baseline	1	(none)	15
Week 12	85	16	127
Week 24	169	128	(First Dose Date of Filgotinib + 14) - Study Day 1 + 1
Analysis Visit	On-Filgotinib Study Day	On-Filgotinib Lower Limit	On-Filgotinib Upper Limit
Week 52*	197	16	≥ 197

* For subjects who were on placebo and re-randomized their analysis window after Week 24 will be assigned according to On-Filgotinib Study Day, On-Filgotinib Lower Limit and On-Filgotinib Upper Limit.

The analysis windows for On-Treatment Healthcare Resource Utilization Questionnaire (HRUQ), Treatment Satisfaction Questionnaire for Medication (TSQM) and ECG data are provided in [Table 3-7](#) and [Table 3-8](#).

Table 3-7. Analysis Visit Windows for On-Treatment HRUQ,TSQM and ECG Data for Subjects who were Initially Randomized to Filgotinib or Adalimumab, and Subjects who were Initially Randomized to Placebo and not Re-randomized

Analysis Visit	Nominal Study Day	Lower Limit	Upper Limit
Baseline	1	(none)	1
Week 12	85	2	127
Week 24	169	128	211
Week 36	253	212	309
Week 52	365	310	≥ 365

Table 3-8. Analysis Visit Windows for On-Treatment HRUQ,TSQM and ECG Data for Subjects who were Initially Randomized to Placebo and Re-randomized

Analysis Visit	Nominal Study Day	Lower Limit	Upper Limit
Baseline	1	(none)	1
Week 12	85	2	127
Week 24	169	128	First Dose Date of Filgotinib - Study Day 1 + 1
Analysis Visit	On-Filgotinib Study Day	On-Filgotinib Lower Limit	On-Filgotinib Upper Limit
Week 36*	85	2	141
Week 52*	197	142	≥ 197

* For subjects who were on placebo and re-randomized their analysis window after Week 24 will be assigned according to On-Filgotinib Study Day, On-Filgotinib Lower Limit and On-Filgotinib Upper Limit.

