For the superiority test of the proportion of subjects who achieve DAS28(CRP) < 2.6 at Week 12, the similar logistic regression analysis with the same model specification as the primary endpoint analysis described in Section 6.2.3 will be adopted for the treatment comparisons. The model will include all treatment groups. The NRI method will be used to impute missing value. Comparison will be made between each filgotinib dose group and placebo group. The p-value from the logistic regression model will be reported for statistical inference. The 2-sided 95% CI of response rate based on normal approximation with the sample variance will be provided for each treatment group. In addition, non-stratified response rate difference along with its 95% CI calculated based on the normal approximation with the pooled the sample variance will be provided. The superiority test of the proportion of subjects who achieve DAS28(CRP) \leq 3.2 or DAS28(CRP) < 2.6 at Week 12 will be performed in the similar way, and the comparison will be made between each filgotinib dose group and adalimumab group.

The change from Baseline in HAQ-DI at Week 12 will be analyzed using the mixed-effects model for repeated measures (MMRM) that includes data at postbaseline visits up to the time point of interest. Subjects that have a baseline value and at least 1 postbaseline value are included in the analysis. The MMRM models will be used to evaluate treatment effect on change score from Baseline, with baseline value, stratification factors, treatment, visit, and treatment by visit interaction included as fixed effects and subject being the random effect. The MMRM model will include all treatment groups. An unstructured variance-covariance matrix will be used. The Kenward-Roger method will be used to estimate the degrees of freedom. Missing change scores due to missing study visits, early withdrawal or treatment reassignment will not be otherwise imputed using the MMRM approach. The least squares (LS) means and 95% CIs of the difference in mean change from Baseline in HAQ-DI between each filgotinib dose group and placebo group from MMRM will be provided.

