Summary statistics of the actual scores and change from baseline in each of the four types of scores of WPAI-RA (absenteeism, presenteeism, work productivity loss, and activity impairment) will be summarized by treatment and visit using descriptive statistics (sample size, mean, SD, median, Q1, Q3, minimum and maximum).

The analyses of absenteeism, presenteeism, and work productivity loss will be based on subjects employed at both baseline and postbaseline visits.

- **HRUQ**

Summary statistics will be provided for all the following parameters by treatment group and visit.

Healthcare resource utilization – Outpatient visits:

— Number and percentage of subjects with any medical visits, and the number of visits related to RA will be provided for the categories:

- Outpatient Healthcare Provider
- Emergency Room
- Chiropractor, Physical or Occupational Therapist

Healthcare resource utilization – Inpatient hospitalization:

— Number and percentage of subject with hospital stays, and number of stays related to RA

— Descriptive statistics for the total number of days in hospital related to RA

— Number and percentage of subject with nursing home or rehabilitation center stays, and number of stays related to RA

— Descriptive statistics for the total number of days in nursing home or rehabilitation center related to RA

- **TSQM**

Descriptive statistics of the scores from each of the 4 domains (Effectiveness, Side Effects, Convenience, and Global Satisfaction) will be presented by treatment group and by visit.

- **Exploratory PRO**

CCI

Plots of proportions of subjects for categorical endpoints and mean \pm SD for continuous endpoints (including each individual component of the ACR response) will be presented over time by treatment.

Additional statistical tests will be performed for the following efficacy endpoints;

- Compare each filgotinib dose group with adalimumab group at week 24 and 52 in proportion of subjects achieving ACR20, $\text{DAS28(CRP)} \leq 3.2$ and $\text{DAS28(CRP)} < 2.6$ using similar logistic regression as described in Section 6.2.3, and in change from baseline in HAQ-DI, SF-36 PCS and FACIT-Fatigue using similar MMRM model as described in Section 6.3.2.

- Compare filgotinib 200 mg group with placebo switching to filgotinib 200 mg group, and filgotinib 100 mg group with placebo switching to filgotinib 100 mg group at Week 52 in change from baseline in mTSS using similar MMRM model as described in Section 6.3.2.

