- Compare filgotinib 200 mg group with placebo switching to filgotinib 200 mg group, and filgotinib 100 mg group with placebo switching to filgotinib 100 mg group at Week 52 in the proportion of subjects having no radiographic progression using similar logistic regression method as described in Section 6.4.2.

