The erosion score and JSN score at baseline will be set to missing if any of the segments that contribute to derive either the erosion score or JSN score is inadequate, respectively. The erosion score and JSN score at postbaseline visits will be set to missing if more than 1 segment is inadequate, respectively; otherwise the change score of the missing segment will be imputed in the similar way as mTSS.

The missing joint scores at baseline will be imputed when all of the segments at baseline are adequate and the corresponding joints are scored at Week 24. If the corresponding segment at Week 24 is also adequate, the missing joint change scores at Week 24 will be imputed first using the method described before, and the missing joint score at baseline will be imputed as joint score at Week 24 minus the change in joint score. The mTSS at baseline will be the sum of the scores after imputation. The mTSS at postbaseline visits will be derived as change in mTSS plus baseline mTSS. The erosion score and JSN score at baseline and postbaseline visits will be derived in the similar way as mTSS.

Step 3 is to identify which reader pair will be used to derive final mTSS, erosion score and JSN score when an adjudicated read is present. The selection is made at Week 24 based on changes in mTSS as specified below and will be applied to all the visits.

- If both readers and adjudicator have change in mTSS available, the selected reader will be the one whose change in mTSS is closest to that of adjudicator. If the differences of change in mTSS comparing to adjudicator are the same for both readers, then both readers will be selected.
- If adjudicator's change in mTSS is available, but one of the readers' change in mTSS is missing, then the other reader will be selected.

Step 4 is to derive the final mTSS and final change in mTSS at a given timepoint. In the case of not adjudicated subjects the final mTSS will be the mean of the mTSS generated by the 2 readers. For the final change in mTSS, the change from baseline in mTSS will first be calculated for the 2 readers separately, and the final change score will be the mean of these two change scores. In the case of adjudicated subjects the final mTSS and final change in mTSS will be the mean of the mTSS and change in mTSS generated by the selected reader(s) at step 3 and the adjudicator respectively. The final erosion score, JSN score, and change in erosion and JSN score will be derived in the similar way as mTSS.

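### The Week 52 mTSS and no-progression comparisons of continuous filgotinib with placebo-to-filgotinib name no common baseline; under the Section 3.8.2 reset they set about 52 weeks of change against about 28

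*SAP*

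**What the plan says.** SAP Section 6.4.2 ends with additional Week 52 tests. One compares the "filgotinib 100 mg group with placebo switching to filgotinib 100 mg group at Week 52 in change from baseline in mTSS", with a matching 200 mg comparison, using a model like the MMRM of Section 6.3.2. Another compares the same pairs "at Week 52 in the proportion of subjects having no radiographic progression using similar logistic regression method". Neither names a baseline.

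The general rule is in SAP Section 3.8.2: "For subjects who were on placebo and then re-randomized, the baseline after Week 24 will be the last nonmissing value obtained" on or before the first filgotinib dose. mTSS has its own version of that rule: "The mTSS baseline value will be derived based on the measurements collected on or prior to the first dose date of filgotinib + 14 days". Subjects on continuous filgotinib keep the study-start baseline.

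The visit windows follow the same split:
- "Table 3-4. Analysis Visit Windows for On-Treatment mTSS for Subjects who were Initially Randomized to Filgotinib or Adalimumab" (the title continues to placebo subjects who were not re-randomized) places Week 52 at Study Day 365.
- "Table 3-6. Analysis Visit Windows for On-Treatment mTSS data for Subjects who were Initially Randomized to Placebo and Re-randomized" places Week 52 at On-Filgotinib Study Day 197.

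The Section 6.3.2 model is fitted "with baseline value, stratification factors, treatment, visit, and treatment by visit interaction included as fixed effects", so it has a single baseline covariate. Appendix 3 says of the reader pair: "The selection is made at Week 24 based on changes in mTSS as specified below and will be applied to all the visits".

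**The concern.** A comparison of early with delayed start on joint structure should show what the delay cost. That cost is the progression during the 24 weeks on placebo. If the switchers' change is measured from a film taken around the switch, that progression is subtracted out, and their 28 weeks on filgotinib are set against 52 weeks in the continuous arm. The early-start advantage disappears if filgotinib fully halts progression, and it can change sign if some progression continues. The no-progression rate in the switch arms rises for the same reason.

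The reset also fits the model poorly. Switchers would have one postbaseline mTSS visit (Week 52) instead of three (Weeks 12, 24 and 52). The alternative is to mix changes from two baselines in one subject, with no rule for the covariate.

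Timing adds to the case for settling this in advance. SAP Section 2.2 has a sponsor team review unblinded Week 24 efficacy results. The placebo arm's Week 24 mTSS change approximates the gap between the two readings, so an open baseline could be chosen after its approximate effect is known.

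**Working it through.** **Plan's own figure.** SAP Section 1.3 assumes a Week 24 mTSS difference of 0.4, SD 1.85, 90% power and two-sided 0.05. Then n = 2 × (1.960 + 1.282)² × 1.85² / 0.4² = 450 per group after rounding up, and power at 450 is 90.0%. The figure reproduces and is not in dispute; 0.4 and 1.85 are reused below.

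**Time spans**, from Tables 3-4 and 3-6:
- Continuous filgotinib: (365 − 1)/7 = 52 weeks.
- Switchers under the reset: (197 − 1)/7 = 28 weeks, or (196 − 14)/7 = 26 weeks if the baseline film is taken at the +14-day limit.

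**Notation.** r is the mean mTSS change per 24 weeks on continuous filgotinib. s is the switchers' rate per 24 weeks after the switch. Neither is in the documents; r from 0 to 0.4 is assumed, with linear progression.
- Continuous at Week 52: r × 52/24
- Switch from Day 1: (r + 0.4) + s × 28/24
- Switch from the reset baseline: s × 28/24

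**Contrasts (continuous minus switch; negative favours early start).**
- Day 1: (r − s) × 28/24 − 0.4, which is −0.40 when s = r
- Reset: r × 52/24 − s × 28/24, which is +r when s = r
- Reset minus Day 1: 0.4 + r, whatever the value of s

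**Precision.** The placebo arm is reassigned 1:1, so a switch arm has at most 450/2 = 225 subjects. With SD 1.85 assumed at Week 52, SE = 1.85 × √(1/450 + 1/225) = 0.151. The Day 1 contrast has z = −0.40/0.151 = −2.65, about 75% power.

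| r (= s) | Continuous | Switch, Day 1 | Switch, reset | Day 1 contrast | Reset contrast | Reset z |
|---|---|---|---|---|---|---|
| 0 | 0.000 | 0.400 | 0.000 | −0.40 | 0.00 | 0 |
| 0.1 | 0.217 | 0.617 | 0.117 | −0.40 | +0.10 | 0.66 |
| 0.2 | 0.433 | 0.833 | 0.233 | −0.40 | +0.20 | 1.32 |
| 0.3 | 0.650 | 1.050 | 0.350 | −0.40 | +0.30 | 1.99 |
| 0.4 | 0.867 | 1.267 | 0.467 | −0.40 | +0.40 | 2.65 |

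Under the reset, the chance of a nominally significant result favouring continuous filgotinib falls from about 75% to 2.5% or less. The chance of one against it runs from 2.5% to 75% over the range of r.

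**When the sign reverses.** The reset contrast is positive only if r > 0 and s < (52/28) r = 1.86r. At r = 0.2 and s = 0.4 it is 0.433 − 0.467 = −0.03: the advantage is almost gone but not reversed.

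**No progression** (change ≤ 0.5, the Section 6.4.2 Week 24 threshold; normal, SD 1.85, r = s = 0.2):
- Continuous: Φ((0.5 − 0.433)/1.85) = 51.4%
- Switch from Day 1: Φ((0.5 − 0.833)/1.85) = 42.9%, a difference of +8.6 points from unrounded rates
- Switch from reset: Φ((0.5 − 0.233)/1.85) = 55.7%, a difference of −4.3 points

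**The case against.** The best counter-argument is that Day 1 was meant all along, and several passages support it. The Section 6.3.2 model suits three visits measured from one baseline. Appendix 3 picks readers on the Week 24 change, imputes missing baseline joints from Week 24 and has no algorithm for a second mTSS baseline. The loss-of-response rule for Weeks 30 to 52 is stated from Day 1 in the protocol and from Baseline in the SAP, so in that rule the SAP's term means Day 1 even for switchers. Where the safety sections want the second baseline (for example SAP 7.2.2.1), they name it; the Week 52 mTSS tests do not. A film near the switch can also serve as both the Week 24 outcome and the start of an on-filgotinib summary, so that overlap is not a contradiction in itself.

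This shows that Day 1 is a plausible intention. It does not remove the stated rule. Section 3.8.2 gives mTSS its own reset clause, mTSS is an efficacy endpoint, and Week 52 is the only mTSS visit in Table 3-6 after the switch. A programmer following the text would apply the reset.

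The objection to the size of the effect partly stands. Week 14 non-responders stop study drug, so 225 is a ceiling and the switchers are a selected group to whom the whole-arm 0.4 need not apply. If, as an assumption, 60% were re-randomized (135 per switch arm against 450), SE is about 0.18, the Day 1 z is about −2.2, and the reset z at r = 0.3 is about 1.65. The figures are illustrative. Selection changes the size of the shift but does not bring the two baselines together.

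**Conclusion.** The concern holds. The plan supports two readings of these Week 52 comparisons, and the one that follows its stated baseline rule compares unequal spans and discards the placebo-period damage. The gap between the readings is the switchers' mean Week 24 change on placebo: 0.4 to 0.8 points for r from 0 to 0.4, if the planned 0.4 applies to them. Whether the sign reverses depends further on linearity and the post-switch rate; the z values and percentages also depend on SD 1.85 at Week 52 and full retention, and the percentages on normality.

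This should be fixed, but its reach is limited. The tests are nominal and outside the Section 3.5 hierarchy. The primary analysis and the key secondary analyses, including mTSS at Week 24, do not change. Confidence is medium because the intended baseline cannot be established from the documents.

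**What to change.** Add one sentence to SAP Section 6.4.2: for the Week 52 switch comparisons of mTSS change and of no radiographic progression, both groups use the original study-start mTSS baseline, that is, the first mTSS baseline rule in Section 3.8.2. Add a cross-reference in Section 3.8.2 stating that the post-Week 24 baseline does not apply to these tests. Report the switch arms' 28-week on-filgotinib change separately, as descriptive only.

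The cost is that sentence and the cross-reference. The baseline, Week 24 and Week 52 films are already scheduled, so no new data are needed.

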6.5. Changes From Protocol-Specified Efficacy Analyses

The following changes were made from the protocol-specified efficacy analyses:

- It has been observed from the blinded data that the enrollment rate is low in some combinations of stratification factors, which will result in the small cell counts for the stratified Cochran-Mantel-Haenszel test adjusted for the stratification factors. The logistic regression analysis with treatment and stratification factors in the model will be used instead to analyze binary endpoints.
- The following endpoints have been updated as key secondary efficacy endpoints in Section 6.3.1 and included in the hierarchy testing in Section 3.5, in order to support inclusion in the label.
 - Change from baseline in SF-36 physical component summary (PCS) at Week 12
 - Change from baseline in FACIT-Fatigue at Week 12
- Given the importance of determining the lowest effective dose for filgotinib in RA, the hierarchical ordering has been updated in Section 3.5 to test filgotinib 100 mg immediately after each test for filgotinib 200 mg (including the primary endpoint and each of the key secondary endpoints).
- Given the importance of achieving very low disease activity $\text{DAS28(CRP)} < 2.6$ in RA therapy, the testing for comparison of filgotinib with placebo on $\text{DAS28(CRP)} \leq 3.2$ is removed from the hierarchy list, and the testing for comparison of filgotinib with adalimumab on $\text{DAS28(CRP)} < 2.6$ at week 12 is added to the hierarchy list. In addition, the comparison of filgotinib with placebo on $\text{DAS28(CRP)} < 2.6$ is evaluated at Week 12 prior to the specified non-responder assessment and start of standard of care therapy at Week 14.

